requirement that at least 80% of base positions reach 20X coverage. Genetic variation will be called using GATK3 (Broad Institute) and variants will be loaded into a custom software analysis application (Codicem, HudsonAlpha) which will annotate variants with relevant information in order to aid in variant curation and interpretation. Variant classification will be determined according to the guidelines set forth by the American College of Medical Genetics and Genomics (Richards *et. al.*, 2015, PMID: 25741868). Variants that are classified as pathogenic, likely pathogenic, or of uncertain significance will be included in a research report and PerkinElmer, EGL-Eurofins, or HudsonAlpha CSL will perform Sanger confirmation, where validation will take approximately 28 days. Variants of interest to the analysts will be discussed by the Variant Review Committee (consisting of neonatologists, medical geneticists, nurse coordinators, GCs, research scientists, ethicists, etc.) to determine whether they should be returned. Variants deemed to be returnable to participants will be written into a genetic counseling report generated by GCs at HudsonAlpha, which, along with the CAP/CLIA-certified Sanger validation report, if available, will be returned to the participant family by a GC or healthcare provider, and placed in the proband's medical record.

(2) University of Alabama at Birmingham (UAB) Women & Infants Center and Children's of Alabama (COA)

Located in the largest metropolitan region in Alabama, UAB Women & Infants Center has a 120 bed level IV NICU with ~1,500 admissions per year and is physically connected to Children's of Alabama (COA), which has a 40 bed NICU and a 20 bed cardiovascular ICU, with ~400 admissions per year. The Division of Neonatology is directed by [name] (UAB Site PI), and includes 15 attending neonatologists. The NICU is also the site of an active medical genetics consultation service including [name]. A chart review of 2017 UAB admissions indicated that 47% were African American and 8% were Hispanic.

(i) Responsibilities

- Identify potential participants in the nursery or inpatient setting using the inclusion/exclusion criteria outlined in the study protocol
- Obtain consent from interested participants
- Collect W9 from parents/caregivers, so they may be paid for their participation in the clinical trial
- Collect blood specimens from the enrolled proband and parents, if available

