In this non-inferiority trial, we aim to compare technology-assisted community-based WGS result delivery by healthcare providers with formal genetic counseling by genetic counselors (GCs). The clinical trial will include parents/caretakers of newborns who undergo WGS. We estimate that 800 parents/caregivers will be enrolled into the clinical trial. Given the complexity of secondary findings and their implications, the parents of all children with secondary findings in the American College of Medical Genetics and Genomics (ACMG) gene list will be provided with formal genetic counseling (standard of care) and will thus be excluded from the clinical trial. We estimate that ~1.5% of sequenced probands will have such findings. Families enrolled before and after the trial period, (the trial is slated to end in January 2021, contingent on whether a no cost extension is to be awarded) will receive results from a GC.

3.e.1 Participant Randomization

Randomization will occur centrally once the WGS results are available and clinical summaries of results are created, ~45-90 days after enrollment, using a computer-generated random number generator. The unit of randomization will be at the family level. Permuted block randomization with varying block size will be utilized. Randomization will be stratified by site and type of WGS result (positive/inconclusive/no finding). Participating families will be assigned to one of the two study arms in a 1:1 ratio. The randomization status of a participant family will be communicated to a site at the same time that the results and clinical summary/family-friendly report are provided to the site, and the site is notified that results are ready to be returned. The Randomization Binder will be kept by [name], lead GC at HudsonAlpha, and will be communicated to the sites by uploading the result file within GG to the site coordinator and to the disclosing health care provider, if known. When files are uploaded, a note will be made of the randomization status. The randomization status of each case will also be documented and tracked in a secure, password-protected excel file outside of Genome Gateway, which will not be accessible to the rest of the study team.

3.e.2 Implementation of the Intervention

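### The randomisation binder sits with the organisation that interprets results, writes the reports and releases cases, so allocation concealment is not assured

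*Combined protocol and SAP*

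**What the plan says.** Section 3.e.1 of the protocol covers the randomisation. On timing: "Randomization will occur centrally once the WGS results are available and clinical summaries of results are created". On generation: "using a computer-generated random number generator". On the scheme: "Permuted block randomization with varying block size will be utilized", stratified by site and by result type (three levels), with a 1:1 ratio between arms. On custody: "The Randomization Binder will be kept by [name], lead GC at HudsonAlpha". The same section describes a password-protected tracking file that the rest of the study team cannot open.

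Other sections give HudsonAlpha the steps around assignment:

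- The entry (1) HudsonAlpha Institute for Biotechnology makes it responsible for interpreting variants, for leading the variant review committee and for the counseling letters. It adds: "Variants deemed to be returnable to participants will be written into a genetic counseling report generated by GCs at HudsonAlpha".
- Section 3.e.2 has HudsonAlpha counselors prepare the family report in both arms, and review the provider-arm recordings.
- Appendix 15 has a HudsonAlpha counselor send the message that tells the site a case is ready and which arm it is in.

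No section says who generates the sequence, what the block sizes are, what the binder contains, or whether result type and trial eligibility are fixed before the assignment is seen. The SAP adds nothing on these points.

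**The concern.** Concealment depends on keeping the next assignment from anyone who can still influence which family receives it. Here the family has already consented, but three things can remain open when its result is known: the order in which waiting cases in a stratum are randomised, the label of a borderline result, and whether a finding counts as a secondary finding that takes the family out of the trial. The organisation that holds the binder has a part in all three.

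Labels can involve judgement. Section 3.c has the review committee decide how far a finding explains the phenotype. The training slides in Appendix 6 use a PALB2 case that is a diagnostic result of uncertain meaning and also carries adult cancer risk.

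The comparison is open-label, and the primary outcome (GCOS) is self-reported. The SAP also draws conclusions by result type, and did not show non-inferiority on GCOS for pathogenic results. If families likely to score low were directed to the counselor arm, the counselor-minus-provider difference would shrink and non-inferiority would look easier to show. The opposite steering would work against it.

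**Working it through.** The documents give no predictability figure, so there is nothing to reproduce. The calculation below is illustrative, and block sizes are assumed throughout.

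**Number of strata.** Section 3.c.1 names five recruiting institutions and section 3.e.5 refers to four sites. With three result types that is 15 or 12 strata.

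- Planned size 800 (section 3.e): 800/15 ≈ 53 or 800/12 ≈ 66 families per stratum, if strata are equal.
- Analysed size is not stated. Assuming equal arms, N ≈ (2 × 1.97 × s/(U − d))², where s is the root mean square of the two SDs, U the reported upper bound and d the mean difference. For GCOS, s = 14.36 and U − d = 4.83 − 0.75 = 4.08, so N ≈ 193. For PUGS, s = 6.63 and 1.22 + 0.63 = 1.85, so N ≈ 200. For PRU, s = 20.19 and 10.13 − 4.47 = 5.66, so N ≈ 198. At about 195, 15 strata hold about 13 families each.

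**Case A: the binder holds a forward list.** Its holder knows every upcoming assignment (100%).

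**Case B: the binder holds only past assignments.** The simplest strategy is to guess the arm that is behind in the stratum, and to guess at random when the arms are level. The Blackwell–Hodges expectation of correct guesses in a block of size 2m is m + (2^(2m)/C(2m,m) − 1)/2:

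- size 2: 1 + (4/2 − 1)/2 = 1.5, or 75.0%
- size 4: 2 + (16/6 − 1)/2 = 2.833, or 70.8%
- size 6: 3 + (64/20 − 1)/2 = 4.1, or 68.3%
- size 8: 4 + (256/70 − 1)/2 = 5.329, or 66.6%

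For mixed sizes, divide total expected correct guesses by total length. For 4 and 6 this is (2.833 + 4.1)/10 = 69.3%. Simulation with the last block cut off at the stratum size gives:

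| Block sizes (assumed) | Long run | 53 per stratum | 13 per stratum |
|---|---|---|---|
| 2, 4 | 72.2% | 72% | 70% |
| 2, 4, 6 | 70.3% | 70% | 68% |
| 4, 6 | 69.3% | 69% | 67% |
| 4, 6, 8 | 68.1% | 68% | 66% |

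Results for 66 per stratum are within half a percentage point of those for 53. Varying the block size therefore leaves the guess rate at about 66–70%, or 72% for the shortest mix in larger strata. Chance is 50%.

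**Effect on the arm difference.** Suppose a fraction f of families differ by D points from others in their stratum, and someone tries to send them all to one arm and succeeds with probability p. Each arm has half the families, so the shift is 2f(2p − 1)D. With f = 0.05 and D = 10 (both illustrative), 2 × 0.05 × 10 = 1.0, and:

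- p = 0.66: 0.32 points
- p = 0.70: 0.40 points (p = 0.72: 0.44)
- p = 1: 1.0 point

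Someone who acted only when the stratum was unbalanced would be right 77–90% of the time, a shift of 0.54–0.80 points. That requires a suitable case to be waiting at the right moment.

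For comparison, the SAP reports a GCOS difference of 0.75, an upper bound of 4.83 and a margin of 10. Adding the full point gives 5.83, still below 10.

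**The case against.** The strongest reply is that the plan already has real safeguards. Randomisation is described as central and computer-generated. It comes about 45–90 days after enrollment, so foreknowledge cannot affect who consents. Result type should already be determined, because results and summaries must exist first. Variants are classified under ACMG guidelines, and a committee of neonatologists, geneticists, nurses, ethicists and others decides what is returned. The secondary-finding exclusion follows a published gene list and is expected to affect about 1.5% of probands, who leave the trial and are not placed in an arm. Stratifying by result type also balances the arms on the most obvious marker of complexity. Reordering needs two cases waiting in the same stratum, and results are due at 3 months plus or minus 1 month. With about 13 families per stratum that would be uncommon.

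Most of this stands, and it is why the effect is probably small. It does not settle custody. Central generation does not say who can see the sequence. The closed file keeps others out, but the concern is the person who has access. The committee shares decisions on labels, but nothing gives it control over the order of randomisation.

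A reader might infer that upcoming assignments are known and concealment is lost. The documents do not support that, because the binder may be only a record of assignments already made. Nor do they show that the lead counselor personally sets strata or times releases. Those tasks belong to HudsonAlpha counselors and the committee, and names are removed, so overlap cannot be checked.

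**Conclusion.** The point holds as a weakness of procedure. Custody of the allocation record is not separated from interpretation, reporting and release, and assignment follows knowledge of the result, so concealment is not assured. The binder's holder knows the next assignment if there is a forward list (not stated), and otherwise can guess it about 66–70% of the time under assumed block sizes. What can be influenced is limited to order within a stratum, borderline labels and the secondary-finding exclusion.

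A reader might take 1 point as the expected bias. That is the ceiling under the illustration, with every steered family reaching the intended arm; at the guess rates the shift is about 0.3–0.4 points. Neither figure would change the combined GCOS conclusion against a 10-point margin. The sizes rest on 5% of families, a 10-point difference and equal strata, none of which the documents give. Nothing shows that steering took place.

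**What to change.** In section 3.e.1, name the UAB trial statistician (UAB biostatistics) as the person who generates and holds both the sequence and the stratum-level log. Naming the data coordinating center would not be enough, because section 2 makes that a partnership of UAB and HudsonAlpha. For each case, HudsonAlpha submits family ID, site, locked result type and secondary-finding status with a timestamp. It receives one assignment and relays it, without access to the sequence or the log. State what the binder contains.

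The SAP already reports results. If assignment is complete, the trial report should say what the binder held, who generated the sequence, the block sizes, and whether result type and eligibility were fixed before each assignment was seen.

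The cost is a short request step and perhaps a day's delay per assignment. UAB biostatistics already receives the de-identified research data (section 3.n.1), so no new partner is needed.
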